12.6.3. Definition of Cardiovascular Events

Cardiovascular Events (CV) Definition:

Investigators will be required to fill out the specific CV event page of the CRF for the following AEs and SAEs:

- Myocardial infarction/unstable angina
- Congestive heart failure
- Arrhythmias
- Valvulopathy
- Pulmonary hypertension
- Cerebrovascular events/stroke and transient ischemic attack
- Peripheral arterial thromboembolism
- Deep venous thrombosis/pulmonary embolism
- Revascularization

12.6.4. Recording of AEs and SAEs

AEs and SAE Recording:

- When an AE/SAE occurs, it is the responsibility of the investigator to review all documentation (e.g., hospital progress notes, laboratory, and diagnostics reports) relative to the event.
- The investigator will then record all relevant information regarding an AE/SAE in the CRF
- It is not acceptable for the investigator to send photocopies of the subject's medical records to GSK in lieu of completion of the GSK, AE/SAE CRF page.
- There may be instances when copies of medical records for certain cases are requested by GSK.
 In this instance, all subject identifiers, with the exception of the subject number, will be blinded on the copies of the medical records prior to submission of to GSK.
- The investigator will attempt to establish a diagnosis of the event based on signs, symptoms, and/or other clinical information. In such cases, the diagnosis will be documented as the AE/SAE and not the individual signs/symptoms.
- PRO questionnaires and the collection of AE data are independent components of the study.
- Responses to each question in PRO questionnaire will be treated in accordance with standard scoring and statistical procedures detailed by the scale's developer.
- The use of a single question from a multidimensional health survey to designate a cause-effect relationship to an AE is inappropriate.

12.6.5. Evaluating AEs and SAEs

Assessment of Intensity

The investigator will make an assessment of intensity for each AE and SAE reported during the study and will assign it to one of the following categories:

- Mild: An event that is easily tolerated by the subject, causing minimal discomfort and not interfering with everyday activities.
- Moderate: An event that is sufficiently discomforting to interfere with normal everyday activities
- Severe: An event that prevents normal everyday activities. an AE that is assessed as severe will not be confused with an SAE. Severity is a category utilized for rating the intensity of an event; and both AEs and SAEs can be assessed as severe.
- An event is defined as 'serious' when it meets at least one of the pre-defined outcomes as described in the definition of an SAE.

Assessment of Causality

- The investigator is obligated to assess the relationship between study treatment and the occurrence of each AE/SAE.
- A "reasonable possibility" is meant to convey that there are facts/evidence or arguments to suggest a causal relationship, rather than a relationship cannot be ruled out.
- The investigator will use clinical judgment to determine the relationship.
- Alternative causes, such as natural history of the underlying diseases, concomitant therapy, other
 risk factors, and the temporal relationship of the event to the study treatment will be considered
 and investigated.
- The investigator will also consult the Investigator Brochure (IB) and/or Product Information, for marketed products, in the determination of his/her assessment.
- For each AE/SAE the investigator must document in the medical notes that he/she has reviewed the AE/SAE and has provided an assessment of causality.
- There may be situations when an SAE has occurred and the investigator has minimal information to include in the initial report to GSK. However, it is very important that the investigator always make an assessment of causality for every event prior to the initial transmission of the SAE data to GSK.
- The investigator may change his/her opinion of causality in light of follow-up information, amending the SAE data collection tool accordingly.
- The causality assessment is one of the criteria used when determining regulatory reporting requirements.

Follow-up of AEs and SAEs

- The investigator is obligated to perform or arrange for the conduct of supplemental measurements and/or evaluations as may be indicated or as requested by GSK to elucidate as fully as possible the nature and/or causality of the AE or SAE.
- The investigator is obligated to assist. This may include additional laboratory tests or investigations, histopathological examinations or consultation with other health care

- professionals.
- If a subject dies during participation in the study or during a recognized follow-up period, the
 investigator will provide GSK with a copy of any post-mortem findings, including
 histopathology.
- New or updated information will be recorded in the originally completed CRF.
- The investigator will submit any updated SAE data to GSK within the designated reporting time frames.

12.6.6. Reporting of SAEs to GSK

SAE reporting to GSK via electronic data collection tool

- Primary mechanism for reporting SAEs to GSK will be the electronic data collection tool
- If the electronic system is unavailable for greater than 24 hours, the site will use the paper SAE data collection tool and fax it to the SAE contact.
- Site will enter the serious adverse event data into the electronic system as soon as it becomes available.
- The investigator (or subinvestiagtor) will mark a check against 'reviewed' box in the lower part of the eCRF page within 72 hours after reporting of SAE to ensure that the causality of AE has been reviewed.
- After the study is completed at a given site, the electronic data collection tool (e.g., InForm system) will be taken off-line to prevent the entry of new data or changes to existing data
- If a site receives a report of a new SAE from a study subject or receives updated data on a previously reported SAE after the electronic data collection tool has been taken off-line, the site can report this information on a paper SAE form or to the SAE contact by telephone.
- Contacts for SAE receipt can be found at the beginning of this protocol on the Sponsor/Medical Monitor Contact Information page.

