7.4.1.1. Time period and Frequency for collecting AE and SAE information

• AEs and SAEs will be collected from the start of Study Treatment until the follow-up contact (see Section 7.4.1.3.), at the timepoints specified in the Time and Events Table (Table 10).

- Medical occurrences that begin prior to the start of study treatment but after obtaining informed consent may be recorded on the Medical History/Current Medical Conditions section of the CRF.
- Any SAEs assessed as related to study participation (e.g., protocol-mandated procedures, invasive tests, or change in existing therapy) or related to a GSK product will be recorded from the time a subject consents to participate in the study up to and including any follow-up contact.
- All SAEs will be recorded and reported to GSK within 24 hours, as indicated in Section 12.6.

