7.4.4.3. Prompt Reporting of Medical Device Incidents to GSK

- Medical device incidents will be reported to GSK within 24 hours once the investigator determines that the event meets the protocol definition of a medical device incident.
- Facsimile transmission of the "Medical Device Incident Report Form" is the preferred method to transmit this information to the SAE contact information.
- The same individual will be the contact for receipt of medical device reports and SAEs.
- In the absence of facsimile equipment, notification by telephone is acceptable for incidents, with a copy of the "Medical Device Incident Report Form" sent by overnight mail.

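### The paper back-up for SAE reports is triggered only after more than 24 hours of electronic outage, although SAEs are due within 24 hours

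*Protocol*

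**What the plan says.** Section 7.4.1.1 of the protocol sets the deadline and names the procedure: "All SAEs will be recorded and reported to GSK within 24 hours, as indicated in Section 12.6" (Appendix 6).

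Section 12.6.6, within Appendix 6, gives the routes:

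- Main route: "Primary mechanism for reporting SAEs to GSK will be the electronic data collection tool".
- Back-up during the study: "If the electronic system is unavailable for greater than 24 hours, the site will use the paper SAE data collection tool", to be faxed to the SAE contact.
- When the system returns: "Site will enter the serious adverse event data into the electronic system as soon as it becomes available".
- Once a site has finished and the tool has been shut down: "the site can report this information on a paper SAE form or to the SAE contact by telephone".

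The section closes by saying that the contacts for SAE receipt are listed at the front of the protocol. Appendix 6 does not itself restate the 24-hour limit for SAE reports, and Section 7.4.1.1 does not say when the 24 hours begin.

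**The concern.** A back-up route is useful only if it opens before the deadline it protects. Here the stated trigger, more than 24 hours of downtime, exceeds the full time allowed for the report. A site could follow the outage instruction as written, wait for the trigger, and still have a late report.

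What is at stake is timely receipt of SAEs. Section 7.4.1.5 treats prompt notification as essential to the sponsor's legal and ethical duties. Appendix 2 relies on ongoing review by the sponsor's internal safety team as a mitigation for the AEs of special interest, which include death and cardiovascular and thromboembolic events. Late receipt delays that review.

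**Working it through.** The plan states no figure that needs reproducing. The check is timeline arithmetic on two stated durations.

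**Inputs**

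- Deadline: 24 h (Section 7.4.1.1).
- Paper trigger: more than 24 h of unavailability (Section 12.6.6).
- Clock start: not stated. Assumed to be the time the site becomes aware of the SAE.
- Site behaviour: assumed to wait for the trigger and to send nothing before it.
- Frequency and length of outages: not in the documents, so no expected number of late reports can be given.

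**Set-up.** Put the start of the outage at hour 0 and awareness at hour *a* (negative if awareness came before the outage).

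- Deadline = *a* + 24.
- Paper route opens just after hour 24.
- Time left for paper = (*a* + 24) − 24 = *a* hours.

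So when *a* is zero or negative, no time is left.

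**Case 1: SAE known but not entered when an outage of more than 24 h begins (*a* ≤ 0).**

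- *a* = 0: the deadline is hour 24 and paper opens after hour 24, so the report is late.
- *a* = −12: the deadline is −12 + 24 = hour 12. Paper opens after hour 24, which is more than 12 + 24 = 36 h after awareness. Twelve of those hours passed while the system was working, and the trigger did not cause them.

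**Case 2: an outage of 24 h or less.** The paper trigger is never reached, and the report waits for the system to return at hour *L*. Electronic entry on return is on time only if *L* ≤ *a* + 24.

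- *a* = −10, *L* = 20: the deadline is −10 + 24 = hour 14 and the system returns at hour 20. The report is at least 20 − 14 = 6 h late.
- *a* = 0, *L* = 20: the deadline is hour 24 and the system returns at hour 20. Entry on return is on time.

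**Case 3: the outage is counted from the site's own first failed entry, *d* hours after awareness (*d* ≥ 0).** Paper opens more than *d* + 24 h after awareness, so it is late by more than *d* hours. If the system stays down, the deadline is missed for every *d*.

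**Case 4: awareness *a* hours into a known outage, counted from its true start (*a* > 0).** With *a* = 10, the deadline is hour 34 and paper opens after hour 24, leaving just under 10 h. The report can be on time.

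**Other routes in the text.** The paper or telephone option quoted last under Section 12.6.6 applies only after the tool has been shut down at a finished site. Section 7.4.4.3 accepts fax or telephone without any waiting period ("In the absence of facsimile equipment, notification by telephone is acceptable for incidents"), but it covers medical device incidents, which are also due within 24 hours. Neither is an instruction for SAEs in the first 24 hours of an outage.

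**The case against.** The strongest reply is that Section 12.6.6 says when a site must move to paper and does not say that paper is barred before then. The electronic tool is described as the primary route, not the sole one. A site that faxes the paper form at hour 10 of an outage meets Section 7.4.1.1 and breaches nothing in Section 12.6.6. This stands. A reader might infer that the two rules can never both be met; the text does not support that.

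A second reply is that the absence of an interim route cannot be asserted outright. The contact page to which Section 12.6.6 refers was not available for review, and the Study Reference Manual is not among the documents. Section 7.4.4.3 also says that the same individual receives device reports and SAEs, so a contact reachable by fax and telephone exists during the study. This limits the claim to the text available. It does not remove the mismatch, because Section 7.4.1.1 sends sites to Appendix 6 for the procedure, and the trigger stated there is too late.

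Three other stronger readings also fail:

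- **Every SAE during an outage is late.** Case 4 shows otherwise.
- **Review of liver stopping events depends on this route.** Appendix 5 gives those events their own duty to report within 24 hours and does not tie it to the electronic tool.
- **A definite expedited-reporting deadline would be missed.** Section 7.4.1.5 gives no expedited timeline, so no such effect can be shown from the documents.

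**Conclusion.** The point holds in limited form, and the Section 12.6.6 bullet is wrong as written: its trigger is misaligned with the protocol's own deadline. If the clock starts at awareness and the site waits for the trigger, every SAE known but unentered at the start of an outage of more than 24 hours is reported late. A shorter outage also causes a late report when it runs past the deadline. If a site counts downtime from its own first failed entry and the system stays down, paper always opens too late.

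The practical size is unknown, because it depends on how often outages occur and on what sites do while waiting. This is a minor point of safety-reporting procedure. It does not bear on sample size, power, type I error or any efficacy analysis.

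**What to change.** Reconcile the two sections by replacing the outage bullet in Section 12.6.6 with: 'If the electronic system is unavailable, the site will send the paper SAE form to the SAE contact in time to meet the 24-hour limit in Section 7.4.1.1, and will enter the data electronically when the system is available.' This ties the back-up to the existing deadline, adds no new time limit, and keeps later electronic entry.

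The cost is one sentence in Appendix 6 and an occasional duplicate paper form when the system comes back soon after the form has been sent.

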12.7. Appendix 7 - Genetic Research Background

Naturally occurring genetic variation may contribute to inter-individual variability in response to medicines, as well as an individual's risk of developing specific diseases. Genetic factors associated with disease characteristics may also be associated with response to therapy, and could help to explain some clinical study outcomes. For example, genetic variants associated with age-related macular degeneration (AMD) are reported to account for much of the risk for the condition [Gorin, 2012] with certain variants reported to influence treatment response [Chen, 2012]. Thus, knowledge of the genetic etiology of disease may better inform understanding of disease and the development of medicines. Additionally, genetic variability may impact the pharmacokinetics (absorption, distribution, metabolism, and elimination), or pharmacodynamics (relationship between concentration and pharmacologic effects or the time course of pharmacologic effects) of a specific medicine and/or clinical outcomes (efficacy and/or safety) observed in a clinical study.

Genetic Research Objectives and Analyses

The objective of the genetic research is to understand the response to daprodustat. To achieve this objective, the relationship between genetic variants and the followings may be investigated.

- Response to medicine, including daprodustat, ESA, other study medicines or any concomitant medicines;
- Nephrogenic anemia and related conditions susceptibility, severity, and progression

•

Genetic data may be generated while the study is underway or following completion of the study. Genetic evaluations may include focused candidate gene approaches and/or examination of a large number of genetic variants throughout the genome (whole genome analyses). Genetic analyses which will be conducted for this study will utilize data collected in the study and will be limited to understanding the objectives highlighted above. Analyses may be performed using data from multiple clinical studies related to daprodustat to investigate these research objectives.

Appropriate descriptive and/or statistical analysis methods will be used. A detailed description of any planned analyses will be documented in a Reporting and Analysis Plan (RAP) prior to initiation of the analysis. Planned analyses and results of genetic investigations will be reported either as part of the clinical RAP and study report, or in a separate genetics RAP and report, as appropriate.

Study Population

Any subject who is enrolled in the study can participate in the genetic research. Any subject who has received an allogeneic bone marrow transplant must be excluded from the genetic research.

Study Assessments and Procedures

A key component of successful genetic research is the collection of samples during clinical studies. Collection of samples, even when no *a priori* hypothesis has been identified, may enable future genetic analyses to be conducted, align with the purpose of the genetic research, to help understand variability in disease and medicine response.

• A 6 mL blood sample will be taken for DNA extraction. A Blood sample is collected at the baseline visit, after the subject has been randomized and provided informed consent for genetic research. Instructions for collection and shipping of the genetic sample are described in the laboratory manual. The DNA from the blood sample may undergo quality control analyses to confirm the integrity of the sample. If there are concerns regarding the quality of the sample, then the sample may be destroyed. The blood sample is taken on a single occasion unless a duplicate sample is required due to an inability to utilize the original sample.

The genetic sample is labelled (or "coded") with the same study specific number used to label other samples and data in the study. This number can be traced or linked back to the subject by the investigator or site staff. Coded samples do not carry personal identifiers (such as name or social security number).

Samples will be stored securely and may be kept for up to 15 years after the last subject completes the study, or GSK may destroy the samples sooner. GSK or those working with GSK (for example, other researchers) will only use samples collected from the study for the purpose stated in this protocol and in the informed consent form. Samples may be used as part of the development of a companion diagnostic to support the GSK medicinal product.

Subjects can request their sample to be destroyed at any time.

Informed Consent

Subjects who do not wish to participate in the genetic research may still participate in the study. Genetic informed consent must be obtained prior to any blood being taken.

Subject Withdrawal from Study

If a subject who has consented to participate in genetic research withdraws from the clinical study for any reason other than being lost to follow-up, the subject will be given a choice of one of the following options concerning the genetic sample, if already collected:

- Continue to participate in the genetic research in which case the genetic DNA sample is retained
- Discontinue participation in the genetic research and destroy the genetic DNA sample

If a subject withdraws consent for genetic research or requests sample destruction for any reason, the investigator must complete the appropriate documentation to request sample destruction within the timeframe specified by GSK and maintain the documentation in the site study records.

Genotype data may be generated during the study or after completion of the study and may be analyzed during the study or stored for future analysis.

• If a subject withdraws consent for genetic research and genotype data has not been analyzed, it will not be analyzed or used for future research.

• Genetic data that has been analyzed at the time of withdrawn consent will continue to be stored and used, as appropriate.

•

Screen and Baseline Failures

If a sample for genetic research has been collected and it is determined that the subject does not meet the entry criteria for participation in the study, then the investigator should instruct the subject that their genetic sample will be destroyed. No forms are required to complete this process as it will be completed as part of the consent and sample reconciliation process. In this instance a sample destruction form will not be available to include in the site files.

Provision of Study Results and Confidentiality of Subject's Genetic Data

GSK may summarize the genetic research results in the clinical study report, or separately and may publish the results in scientific journals.

12.8. Appendix 8: Definition of and Procedures for Documenting Medical Device Incidents

12.8.1. Definitions of a Medical Device Incident

The detection and documentation procedures described in this protocol apply to all medical devices provided for use in the study (see Section 6.2 for the list of the medical devices).

Medical Device Incident Definition:

- Incident Any malfunction or deterioration in the characteristics and/or performance of a device, as well as any inadequacy in the labeling or the instructions for use which, directly or indirectly, might lead to or might have led to the death of a patient/user/other persons or to a serious deterioration in their state of health.
- Not all incidents lead to death or serious deterioration in health. The non-occurrence of such a
 result might have been due to other fortunate circumstances or to the intervention of health care
 personnel.

It is sufficient that:

- an incident associated with a device happened and
- the incident was such that, if it occurred again, might lead to death or a serious deterioration in health

A serious deterioration in state of health can include:

- life-threatening illness
- permanent impairment of body function or permanent damage to a body structure
- a condition necessitating medical or surgical intervention to prevent one of the above
- fetal distress, fetal death or any congenital abnormality or birth defects

Examples of incidents

- a patient, user, care giver or professional is injured as a result of a medical device failure or its misuse
- a patient's treatment is interrupted or compromised by a medical device failure
- misdiagnosis due to medical device failure leads to inappropriate treatment
- a patient's health deteriorates due to medical device failure

0044 B

12.8.1.1. Documenting Medical Device Incidents

Medical Device Incident Documenting:

- Any medical device incident occurring during the study will be documented in the subject's
 medical records, in accordance with the investigator's normal clinical practice, and on the
 appropriate form.
- For incidents fulfilling the definition of an AE or an SAE, the appropriate AE/SAE CRF page will be completed as described in Appendix 6 (Section 12.6).
- The form will be completed as thoroughly as possible and signed by the investigator before

transmittal to GSK.

- It is very important that the investigator provides his/her assessment of causality to the medical device provided by GSK at the time of the initial report, and describes any corrective or remedial actions taken to prevent recurrence of the incident.
- A remedial action is any action other than routine maintenance or servicing of a device where such action is necessary to prevent recurrence of an incident. This includes any amendment to the design to prevent recurrence.

